C3. Data Sources. a. VA Risk ID Clinical Performance Measures: Outcomes for primary and secondary aims will include four clinical performance measures extracted from VA's EPRP that reflect key practice elements of VA Risk ID: primary suicide screening (sui40 and sui51), secondary suicide screening (sui 2) and the CSRE (csra1). These four measures are currently in pilot status as they are being validated. EPRP measures are routinely abstracted monthly. VA Risk ID EPRP measures at baseline evaluation (month 6). month 10 of Intervention Phase I and month 10 of Intervention Phase II will be used to evaluate the effectiveness of the implementation strategies (primary and secondary aims). A specific advantage of using EPRP performance measures is that the actual abstraction and collection of data occurs independently from the evaluation team and program office. A data use agreement will be obtained to facilitate the use of EPRP data for this QI project. VA Risk ID EPRP Validation Process: VHA and EPRP contractors develop the data collection instruments (abstraction tools), which are programmed into abstraction software. Data are collected monthly by the abstractors for a random sample of Veterans and the contractor monitors for irregular abstraction patterns. Once final quarterly data are received, question level response patterns and scoring algorithms may be reviewed. Inter-rater reliability (IRR) on the measures will also be reviewed at least once a year. Upon the IRR review, additional edits may be made to the data collection instrument. Once the measure and instrument are considered stable and the data is considered reliable, they can move out of a pilot status. We anticipate that by the start of this project, these measures will be out of pilot status as they will have gone through several rounds of testing and revisions. If we encounter unanticipated and significant challenges to validation of EPRP VA Risk ID measures, we will use the RE-AIM domain of "reach" as our primary outcome measure. **b. Corporate Data Warehouse (CDW):** CDW is a database organized into a collection of data domains derived from the VHA electronic health record. It contains records of inpatient and outpatient care including dates and location of care, as well as associated ICD-10 codes. We will use electronically abstracted data to evaluate reach and effectiveness of the clinical innovation. For Exploratory Aim 1, specific sources of CDW data will include: 1) patient socio-demographic characteristics that allow for comparison between Veterans reached and all Veterans eligible for screening 2) patient responses and results from the screens for Depression, PTSD, and C-SSRS that are administered within Mental Health Assistant; 3) note templates containing the CSRE; and 4) Health Factors recording responses to the CSRE and date of CSRE administration. These sources of data will also serve as data sources for Exploratory Aim 3. Additionally, we will gather health factors specific to the suicide prevention safety plan details and dates. Free-text progress notes may also be abstracted if needed. c. IAU, A/F and EF Debriefing Interviews: Semi-structured interviews will be conducted by an independent evaluator monthly with study team members implementing IAU during the three project phases, A/F during Intervention Phases I and II and EF during Intervention Phase II. The purpose of the interviews is to gather information regarding implementation activities, program and implementation modifications, and implementation barriers and facilitators. The independent evaluator will also use this information to complete the A/F and EF Fidelity Checklists (see below). Draft interview guides are included in Appendix 3. d. Key Informant Interviews: Semi-structured interviews will be conducted with primary care (PC) and primary care mental health integration (PCMHI) leadership and providers after each of the three project phases via telephone. Interviews will explore barriers/facilitators to implementation as well as factors that impact the adoption and utility of the implementation interventions. All interviews will be conducted by the independent evaluator to reduce potential bias. Interviews will be audio recorded and recordings will be transcribed. Draft interview guides for each project phase are included in Appendix 3. e. IAU and EF Activity Logs: A/F and EF Adoption Logs: The IAU Activity Log contains the components of IAU and will be completed monthly throughout each study phase by the independent evaluator. The EF Activity Log²⁴ will be completed by facilitators weekly to track the facilitation activities completed for each site receiving facilitation. The A/F and EF Adoption Logs will be completed weekly by the study team member responsible for sending out A/F and EF communications. These data will be used to determine whether sites adopted the implementation interventions. See Appendix 4 for draft logs. f. A/F and EF Fidelity Checklists: Fidelity checklists will be used to ensure that A/F and EF were delivered as intended.

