
C7. Analyses. a. Sample Size and Power Calculations: Power was calculated using the two-sample ttest procedure in Power and Sample Size (PASS 16). As there are two primary EPRP outcomes (sui2 and csra1), alpha is set to 0.025. The FY2018 first quarter numbers for a similar EPRP (sre1, timely SRE if positive PTSD or MDD screen) across 140 facilities was used to obtain an estimated standard deviation for sui2 and csra1 of 0.10. Power was calculated for two scenarios given the preliminary fallout data noted above. Assuming proportions of 0.8 and 0.9 not adequately implementing at month 6 of the run-in phase such that N=112 and N=126 are eligible for randomization at R1, this would provide 80% power to detect a difference in change between A/F and IAU of 0.059, and 0.055, respectively. Regarding secondary aim 1, assuming alpha=0.05, SD=0.10, and facilities eligible for randomization at R2 of 56 and 63, there is 80% power to detect a difference in change between continued A/F and A/F + Facilitation of 0.076 and 0.072, respectively. Given the same assumptions for secondary aim 2 as used for secondary aim 1, the detectable differences in change are the same for examining continued A/F versus discontinued A/F. **b. Primary Aim:** Using linear regression, the primary

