EPRP outcomes of change in sui2 and csra1 from the 6th month of the baseline period to the 10th month of the first interventional phase will each be modeled as a function of group (A/F vs. IAU), the baseline outcome value, the stratification variables of facility complexity (high, medium, low) and baseline performance level (above or below the median average fallout rate), and geographic region (West, Midwest, Southwest, Southeast and Northeast). Inference will be made based on the coefficient associated with the group variable and 97.5% confidence intervals (CI) will be reported (alpha=0.025). A similar analysis will be used to determine the effect of A/F on the change in the EPRP outcome for the primary screeners (sui40 and sui51), with 95% CIs reported. **c.** Secondary Aims: 1). To test the effect of the addition of EF for those who do not implement adequately at end of interventional phase 1, the primary EPRP outcomes of change in sui2 and csra1 from the 10th month of interventional phase 1 (baseline for interventional phase 2) to the 10th month of interventional phase 2 will be modeled as a function of group, the baseline outcome value, the stratification variables and geographic region (if sample sizes allow for control of this variable). Inference will be made based on the coefficient associated with the group variable and 95% CIs will be reported. A similar analysis will be used to determine the effect of the addition of EF on the change in the EPRP outcome for the primary screeners (sui40, sui51), with 95% CIs reported. 2). An analysis similar to that described for secondary aim 1 will be employed to investigate the effect of discontinuing A/F for those who implemented adequately at the end of interventional phase 1. Lastly, we will use a data driven approach to characterize each of the four EPRP outcomes over time for each group outlined in Figure 2 (group 1-6). Mixed effects models with a random intercept and slope will be used to model each of the four EPRP outcomes as a function of categorical group (1-6) and an interaction between group and a Bspline transformation on time (allowing the outcome to vary smoothly over time, using 21-time points, i.e., the 6th baseline month and every month of each interventional phase) such that each group will have its own trajectory. The trajectory for each group will be plotted with pointwise confidence intervals. **d. Exploratory** Aims: *i. Reach*: Reach will be calculated using the following formula: actual number of Veterans screened or evaluated/ actual number of Veterans eligible for screening, calculated cumulatively across all three study phases and all sites. We will calculate reach for each assessment stage of VA Risk ID. We will examine representativeness of patients reached by comparing demographic characteristics and other relevant variables (e.g., settings in which screening was completed) between eligible Veterans who were screened and/or evaluated and those who were not. Given that Veterans are clustered within facility, if the intra-class correlation between Veterans within each facility is estimated to be greater than zero, methods appropriate for clustered data will be employed to compare the variables of interest. For continuous variables, linear mixed models will be used with a random facility effect and non-normal data will be transformed. For binary variables, generalized linear mixed models will be used with a logit link and for categorical variables, random effects multinomial models will be employed. If the ICC is zero, t-tests, Wilcoxon rank-sum, Chi-square or Fisher's exact tests will be used, as appropriate. *ii. Adoption & Implementation Factors:* Key informant interviews will be used to examine factors influencing adoption of the implementation interventions and barriers and facilitators of implementing VA Risk ID to fidelity. All qualitative data sources, including interview transcripts and documents will be compiled and managed using Nvivo V. 9.0 software. We will take a general inductive approach³⁴. Specifically, data analysis will be determined by both the research objectives (i.e., domains of the RE-AIM framework) and multiple readings and interpretation of the raw data (i.e., content analysis). The goal is to establish clear links between the research objectives and the summary findings derived from the raw data. *iii. Effectiveness- Clinical Innovation:* We wish to examine whether Veterans who receive the CSRE are more likely to receive a safety plan within 2 weeks than those who screen positive on the primary screen only. To account for clustering of Veterans within facility, a mixed-effects logistic regression will be used to model the outcome of safety plan within 2 weeks (yes/no) as a function of group (receipt of CSRE/positive on primary screen only) with a random subject within facility effect. Additionally, to determine if receipt of a timely safety plan depends on whether Veterans are considered to be at low, moderate or high acute risk of suicide, this model will be repeated with the addition of a group by (categorical) acute risk interaction. Odds ratios for receipt of CSRE relative to positive on primary screen only will be reported for each level of acute risk with 95% confidence intervals.

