Examining the Effectiveness of an Adaptive Implementation Intervention to Improve Uptake of the VA Suicide Risk Identification Strategy (PEC 19-303)

NCT04243330

October 17, 2024

QUERI RISK ID Statistical Analysis

Primary Aim. Determine if the addition of Audit and Feedback in Phase 1 (February 2021 – November 2021) significantly improved eCSSRS1 and eCSRE1 adherence. To determine the effect of Audit & Feedback on Phase 1, we compared group 6 (Implementation As Usual [IAU] in Phase 1; N=66) to Groups 2, 3, 4, and 5 combined (Audit & Feedback [AF] in Phase 1; N=67). We used all available data and modeled monthly 1) eCSSRS1 and 2) eCSRE1 adherence across the entire study period (January 2021 – March 2024) for each group (IAU and AF). We chose to estimate these trajectories using natural cubic B-spline transformations on time to allow for smoothly changing trajectories and not restrict the estimation to a parametric form (e.g., polynomials). Internal knot selection for the B-splines was based on visible change points in descriptive longitudinal plots – these were November 2021, January 2022, November 2022, and March 2023 (or months 11, 13, 23, and 27). These 4 internal knots result in 5 knot spans and 5 degrees of freedom for each group/outcome combination modeled. Each outcome was then modeled as a function of group, the B-spline transformations, and group by B-spline transformation interactions so that we could estimate a trajectory for each group. These mixed effects models included a random intercept (i.e., random site effect). Contrasts were constructed within each model and were used to estimate the change in adherence for each group from February 2021 – November 2021 and the difference in adherence change between the groups, which was our hypothesis test of interest. These estimated differences in change were reported with 95% confidence intervals (CIs). For both estimates, the difference in change was calculated as the AF group minus the IAU group.

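### Protocol C7.b adjusts the primary comparison for run-in month 6 only; adding the mean of months 1–5 would recover some precision for one degree of freedom

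*Protocol*

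**What the plan says.** Protocol C3.a states that "EPRP measures are routinely abstracted monthly", and the Specific Aims and C5 place six months of IAU before the first randomisation (R1). Of those six months, only the last is used in modelling the primary measures:

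- C7.b takes as outcome the "change in sui2 and csra1 from the 6th month of the baseline period to the 10th month of the first interventional phase" and adjusts for group, the baseline value, complexity, performance level and region.
- C5 forms the performance stratum from each site's average fallout rate in the sixth baseline month.
- The trajectory model in C7.c is fitted "using 21-time points, i.e., the 6th baseline month and every month of each interventional phase".

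The SAP's primary analysis is a different model. It fits monthly eCSSRS1 and eCSRE1 "adherence across the entire study period (January 2021 – March 2024) for each group", with group, splines on time, their interaction and a random site intercept, and tests the difference in change from February to November 2021. It lists no baseline covariate. January 2021 is the one month in its series before Phase 1.

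**The concern.** Under C3.a a monthly site value rests on a random sample of Veterans. Under the measure definitions in Section A, sui2 counts only those with a positive primary screen and csra1 only those with a positive secondary screen, so the sampled denominators shrink at each stage. One month may therefore be an imprecise guide to a site's usual level. Months 1–5 precede randomisation and cannot be affected by assignment, which makes them legitimate covariates. The number of sites is capped (up to 140 in the protocol; 66 + 67 = 133 compared in the SAP), so precision cannot be bought by recruiting more. What is at stake is the width of the interval for A/F versus IAU on both primary outcomes.

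**Working it through.** **1. The plan's own figure.** Inputs from C7.a: "As there are two primary EPRP outcomes (sui2 and csra1), alpha is set to 0.025"; a quarterly figure for a similar measure "was used to obtain an estimated standard deviation for sui2 and csra1 of 0.10"; N = 112 or 126; 80% power. C5 gives 1:1 allocation. A two-sided two-sample t-test (noncentral t) gives detectable differences of 0.0589 (56 per arm) and 0.0555 (63 per arm), against the stated 0.059 and 0.055. The normal approximation agrees: (2.241 + 0.842) × 0.10 × √(2/56) = 0.0583. The figures reproduce. They use no baseline covariate, so they do not depend on which run-in months are used.

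**2. What has to be assumed.** The documents give neither the monthly sample size per site nor any between-month correlation. Two correlation structures are tried. Months are numbered 1–6 (run-in) and 7–16 (Phase I), so the outcome is month 16. With the month-6 value in the model, analysing change or level gives the same group coefficient and residual variance. Total variance is set to 1.

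**3. Structure A: stable site part s plus month noise with lag-1 correlation ρ.** Correlation at lag k is s + (1−s)ρ^k. Let c₆ and c_M be the covariances of month 16 with month 6 and with the mean M of months 1–5.

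- Month 6 alone: V₁ = 1 − c₆².
- Month 6 and M: V₂ = V₁ − (c_M − c₆·cov(M, month 6))² / (var(M) − cov(M, month 6)²).

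Middle case s = 0.5, ρ = 0.5: c₆ = 0.5005, c_M = 0.5001, cov(M, month 6) = 0.5969, var(M) = 0.7225.

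- V₁ = 1 − 0.2505 = 0.7495.
- V₂ = 0.7495 − (0.5001 − 0.2987)² / (0.7225 − 0.3563) = 0.7495 − 0.1108 = 0.6387.
- V₂/V₁ = 0.852, so variance falls 15%. This equals 1/0.852 = 1.17 times the sites, and √0.852 = 0.923, a detectable difference about 8% smaller.

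V₂/V₁ over the grid:

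| s | ρ = 0 | ρ = 0.5 | ρ = 0.8 |
|---|---|---|---|
| 0.3 | 0.862 | 0.925 | 0.975 |
| 0.5 | 0.762 | 0.852 | 0.943 |
| 0.7 | 0.680 | 0.783 | 0.908 |

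The reduction runs from 2% to 32%. If 0.10 is read as the SD left after month-6 adjustment, the middle case moves 0.0589 to 0.0589 × 0.923 = 0.0544 (N = 112).

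**4. Structure B: no permanent site part.** Correlation at lag k is a·φ^k, with a the single-month reliability.

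| φ per month | Fall in variance, a = 0.4 to 0.8 |
|---|---|
| 0.90 | 1% or less |
| 0.95 | 3%–5% |
| 0.98 | 10%–13% |

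With a = 1 (no month noise) the fall is zero.

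**5. Add, do not replace.** With a = 1, using the plain six-month mean *in place of* month 6 makes the detectable difference 2%–6% larger (φ = 0.90 to 0.98). Keeping month 6 and adding M cannot raise the theoretical residual variance. The price is 1 df. The C7.b model has 10 coefficients (intercept 1, group 1, baseline 1, complexity 2, performance 1, region 4), so at N = 112 this is 1/102, about 1% of variance.

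**6. Whether the same idea carries to the SAP model.**

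- *Time-constant covariate.* If γx is added to every month of a site, it cancels in November minus February. In a balanced random-intercept model the contrast is unchanged; a trial fit with the SAP's knots gave the same estimate (−0.1023) and variance (0.01598) with and without it.
- *Earlier start.* The SAP's internal knots are at months 11, 13, 23 and 27 (January 2021 = 1), with none at the February 2021 start of Phase 1. Take a noise-free group difference of zero to month 1, rising 0.1 per month to 1.0 at month 11, then constant. The true February–November change is 1.0 − 0.1 = 0.90. The present window recovers 0.84. A series starting five months earlier recovers 0.63, because one smooth piece spans run-in and Phase 1. A knot at February 2021 mostly removes this, but then leaves a variance gain of only about 9% (independent month noise).

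**The case against.** The strongest reply is that this is a preference and not an error. R1 is randomised, C7.b is a valid analysis, and no document shows that one month is unreliable. The 0.10 SD comes from quarterly data, so a single month may vary more, but by how much is unknown. Structure A assumes a stable part of at least 30%; with fast decay the gain barely covers the lost degree of freedom. The calculation also leaves out complexity, region and the performance stratum, which may already absorb some of the gain. All of this stands, and it is why the size is given as a range.

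The reply also stands on the SAP. A reader might infer that the reported comparison hangs on one month at each end. The SAP text does not support that: no month-6 covariate is listed, and the February and November values are read from a curve smoothed over the whole series. The percentages above therefore apply to the protocol regression and should not be carried over.

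A reader might also infer that the run-in data go wholly unused. They do not: C7.d calculates Reach cumulatively over all three phases. Nor is it shown that the earlier data are free for the SAP outcomes. C3.a speaks of EPRP measures, and the documents do not say whether eCSSRS1 and eCSRE1 exist before January 2021. Finally, the SAP is dated October 2024 and written in the past tense, so any change to it now would be post hoc.

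What the reply does not answer is the protocol model itself: monthly pre-randomisation values of the same measures were to be abstracted, and five of the six months were left out.

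**Conclusion.** The point holds for the protocol as a modest loss of efficiency. EPRP values from run-in months 1–5 enter no model of the primary performance measures, and adding their mean beside month 6 would reduce residual variance by 2%–32% with a stable site component of 30%–70% (middle case 15%), or by 0%–13% with correlation decaying at 0.90–0.98 per month. Both ranges rest on assumed correlations and ignore the other covariates.

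Two stronger conclusions are not supported. The omission does not bias the A/F versus IAU estimate: selection on month 6 brings regression to the mean in both randomised arms alike. And it does not undermine the stated power, which reproduces without any baseline adjustment. It is also tempting to average Phase I months 8–10 as the endpoint. That would change the estimand, could dilute an effect still growing at month 10, and is a separate trade-off that this point does not justify.

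**What to change.** In protocol C7.b, keep the month-6 value and add each site's mean of run-in months 1–5 for the same measure as a second covariate. Leave the month-10 endpoint as it is. The cost is one degree of freedom, a sentence of text, and a pull of five months of routinely abstracted data.

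In the SAP, leave the primary spline model as it stands: do not start its series earlier with the present knots, and do not add a time-constant run-in covariate. If eCSSRS1 and eCSRE1 can be computed before January 2021 (back to August 2020, assuming January 2021 was run-in month 6), report the C7.b-type site-level regression with the run-in mean beside the SAP model, labelled as a post hoc sensitivity analysis. If they cannot, one sentence saying so closes the point.
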